Physical functional assessment tests will be conducted by a trained physical therapist. Participants will complete a 50ft timed walk, TUG test (rise from chair, walk 3m, turn back, and sit in chair), a timed 13 stair climb, and the Chair Raise test (a functional leg strength test-participants stand from chair and sit for 5 repetitions). Postural stability will be calculated as displacement of the body at the level of the waist in 30 second periods as measured by a Sway meter. The Functional Reach test has participants bend at the waist and reach out with one arm as far as they can. Muscle hand grip strength will be measured using the Harpenden Hand Grip dynamometer and hip flexor and knee extensor strength will be assessed by the Push-Pull Muscle Strength dynamometer.

Surveys (Functional self-assessment: Physical Activity Scale for Persons with Physical Disabilities (PASIPD), NIH PROMIS (short forms), and Beck Depression Inventory (BDI). Cognitive assessment battery: mini-mental status, executive function assessment, attention & processing speed assessment, memory assessment, language assessment.). The total time to perform these surveys is about 2.5 hours. *Functional self-assessment battery includes:* the PASIPD, BDI, and the NIH PROMIS short forms of Physical Function, Pain, Fatigue, Global Health, Sleep, and Emotional Distress. Functional self-assessment surveys will be performed by the research assistant. *Cognitive battery includes:* Trail Making Test A & B; Symbol Digit Modalities Test (SDMT); the Digit Span subset of the Wechsler Adult Intelligence Scale-III (DS WAIS-III), verbal memory test & delayed recall subsets of the California Verbal Learning Test-Second Edition (CVLT-II), Category Fluency, the controlled oral word association test (COWAT), and STROOP Color & Word tests. The Mini-Mental Status Exam (MMSE) and Short Blessed Test (SBT) will be performed for screening purposes only. The cognitive battery will be performed by a clinical psychologist or research assistant.

Blood draws for vitamin D and B12 Folate levels will require about 5 ml of blood for each draw. All Vitamin D levels will be determined by Quest Laboratories. B12 Folate levels will be determined by kit assay in [name] core laboratory as part of the CMCSCI. Vitamin D levels will be tested twice to establish baseline values. Vitamin D levels will be tested once a month during the treatment phase for safety monitoring. B12 Folate levels will be tested at baseline and 6 months. Blood draws for immune function tests will take place during dialysis sessions at baseline and 6 months. These tests will require a total of a 43cc draw. Immune function measurements include serum cytokines.

Chart review A chart review will be performed for all participants. The chart reviews will be performed by [name] (PI). No subject time commitment is required for the chart reviews.

3. Describe population to be studied, listing basis for selection or exclusion. Include number to be studied.

Individuals with advanced chronic kidney disease on hemodialysis (HD) will be studied. Thirty participants will be studied: 20 in the treatment group and 10 in the placebo group. Enrolled patients will be randomized into either the treatment or placebo group.

4. If subjects are patients, will conventional therapy or diagnostic procedures be withheld or modified for the purpose of this study?

If participants in this study are patients, conventional therapy or diagnostic procedures will not be withheld or modified. All participants will receive their normal care throughout their involvement in research.

b. List Possible RISKS

1. List possible hazards to subjects and/or investigative personnel from the procedures, drugs, or isotopes to be employed.

The main risk in this study is vitamin D toxicity. Vitamin D toxicity usually manifest first with hypercalcemia, which will be monitored by routine monthly dialysis lab tests. Moderate to severe hypercalcemia can result in symptoms of increased urinary frequency, thirst, nausea, vomiting, confusion, decreased appetite, and muscle weakness. Hypercalcemia will be first managed by adjustment of IV vitamin D (administered according to National Kidney Foundation Guidelines (NKF)) which is titrated by the patient's nephrologist and much more likely to be responsible for hypercalcemia versus oral 25-OH vitamin D. If these measures do not correct hypercalcemia, oral vitamin D supplementation will be discontinued. Efforts to correct hypercalcemia will occur as soon as the calcium levels are rise above the upper limits of normal (10.5 mg/dl) which is usually not associated with the above listed clinical symptoms.

The physical function and health questionnaires are non-invasive. The risks associated with venipuncture include: pain, bruising, swelling, and/or infection at the site of the needle puncture; and rarely fainting may also occur. There is the potential for the subject to experience some mild frustration during the cognitive impairment studies. A trained psychologist will be administering the tests.

2. Include estimates of degree of risk with documentation from recent medical literature.

We do not anticipate any patients to develop vitamin D toxicity due to our careful selection of dosing regimen that was based on previous studies. Vitamin D levels will be monitored each month along with monthly dialysis blood tests that are routinely performed on HD patients. If vitamin D levels rise above 60 ng/ml, (conservative cut off point since most reports of toxicity occur > 80 ng/ml) the frequency of

administering vitamin D will be reduced to once a month which is considered routine maintenance dosing to prevent vitamin D deficiency.

Physical function and health questionnaires, venipuncture, and cognitive assessments present minimal risk.

3. What monitoring or other safety precautions will be taken?

To protect against the any possible side effects of vitamin D supplementation toxicity, subjects' 25-OH vitamin D levels will be monitored. If a subject reaches 25-OH levels ≥ 60 ng/mL, the dose will be immediately lowered. As the PI, I will remain blinded and review monthly calcium levels to monitor for evidence of hypercalcemia. When hypercalcemia is identified, the patient's primary nephrologist will be notified so that appropriate adjustments can be made to correct hypercalcemia. The primary nephrologist's first adjustment will be to decrease the dose of IV vitamin D according NKF guidelines.

To protect against the risk of possible side effects of the blood draw, the study personnel will be trained in phlebotomy. To remove as much frustration as possible during the cognitive tests, a trained psychologist will be administering the tests.

c. Possible Benefits

Describe possible benefits from this study and state whether these benefits will be to experimental subject, to others, or both.

The benefits of vitamin D supplementation could possibly include improved muscular, cognitive, and immune function. Improvement of muscular function may allow for more patient independence on IADLs. Interventions that improve cognitive function may also lead to a healthier, more compliant HD patient. These benefits will be to experimental participants. This research also has the potential to benefit others in the future.

D) PREVIOUS WORK DONE BY YOU OR YOUR COLLABORATORS ON THIS OR RELATED PROJECTS, LISTING PUBLICATIONS.

Prevalence of Mild Cognitive Impairment in HD patients: We have collected data from 40 patients undergoing HD at the James J. Peters VAMC to determine if mild cognitive impairment exists in a healthy population with normal MMSE scores (>24) and no clinical history of stroke. Subjects were all male with a mean age of 64 ± 10 y (range: 45-82y), an education level of 13 ± 2 y, and 80% were non-Caucasian. All subjects underwent a comprehensive neurocognitive battery which captured the domains of memory, language, attention & processing speed, and executive function.

Results of preliminary work: Overall, mild cognitive impairment (MCI) was seen in 34 (85%) of the studied population. MCI was broken down further into amnestic and non-amnestic groupings, with 8 (20%) having amnestic MCI and 26 (65%) having non-amnestic MCI. This follows with the literature that memory is more preserved in this population compared to other domains. Of both the amnestic and non-amnestic groups, multiple domain impairment was seen more frequently than single domain impairment. (Post JB, Jegede AB, Morin K, Spungen AM, Langhoff E and Sano M: Cognitive Profile of Chronic Kidney Disease and Hemodialysis Patients without Dementia. *Nephron Clin Pract* 116: c247-c255, 2010)

Vitamin D deficiency in HD patients: Preliminary data of 39 of the 40 subjects show that 33 (85%) of subjects had 25-OH levels < 20 ng/ml and 6 (15%) had levels ≥ 20 ng/ml with a mean of 12.86 ± 8.03

ng/ml (range: 3.8-37.67 ng/ml). Of this convenience sample, we found a 13 point difference (based on T scores) between those with 25-OH levels < 20 ng/ml and those with levels \geq 20 ng/ml in a test of Executive Function, trending towards significance.

E) SIGNIFICANCE OF THIS RESEARCH.

The outpatient HD unit at the James J. Peters VAMC has grown nearly 15% each year for the past two years and is one of the largest VA dialysis centers. Muscle weakness and cognitive impairment are common among HD patients and likely contributes to the high prevalence of falls in this population. Falls result in increased morbidity, decreased independence, and likely increases mortality. While cognitive impairment can contribute to falls it is also likely to result in poor compliance with complex medical treatments and medication regimens required of HD patients. Information about the possibility of improving immune function in this population could also help with quality of life. Given the safety, low cost of supplementation, and potential clinical benefits of vitamin D treatment, we propose a study to evaluate its role in improving important clinical endpoints.

F) LIST OF KEY BIBLIOGRAPHIC REFERENCES.

1. K/DOQI clinical Practice guidelines for bone metabolism and disease in chronic kidney disease. American Journal of Kidney Disease 42 S1-S201, 2003

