SA1: To compare functional performance benefit between HD participants randomized to vitamin D supplementation and placebo. Function will be measured by the 50ft timed walk, the Timed Up and Go test (TUG), a timed stair climb, the Chair Raise test, the Functional Reach test, postural sway, and muscle handgrip, hip flexor and knee extensor strength.

H1: We hypothesize that a greater proportion of the subjects will demonstrate an improvement in postural sway in the treatment group than in the placebo group.

SA2: To compare cognitive function as measured by neuropsychological testing between HD participants randomized to vitamin D supplementation and placebo.

H2: We hypothesize that a greater proportion of the subjects will demonstrate an improvement in the treatment group than in the placebo group.

SA3: To compare the Self-report of physical activity and quality of life (QOL) between HD participants randomized to vitamin D supplementation and placebo.

H3: We hypothesize that the total score on the Physical Activity Scale for Persons with Physical Disabilities (PASIPD) and the QOL scores will significantly improve in the treatment groups versus no change in the control group.

SA4: To compare immune function between HD participants randomized to vitamin D supplementation and placebo.

H4: We hypothesize that immune function will be increased in the treatment group versus no change in the control group.

B) BRIEF REVIEW OF RESULTS OF OTHERS AND CURRENT STATE OF KNOWLEDGE

Pathophysiology and Management of Vitamin D and Deficiency in HD Patients:

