We propose to perform a prospective, randomized, double-blind placebo controlled trial. Patients will be included if they are: 1) receiving outpatient hemodialysis at the James J. Peters VAMC, 2) receiving IV vitamin D therapy according to National Kidney Foundation guidelines, 3) between the ages of 45-89 years, 4) a veteran outpatient or stable community living center patient, and 5) able to ambulate independently or with an assistive device for at least 20 feet. Exclusion criteria include: 1) 25-OH vitamin D level \geq 25 ng/ml, 2) hypercalcemia, 3) active malignancy within 6 months, 4) receiving intravenous antibiotics for infection, 5) history of dementia, 6) hemoglobin $<$ 8.5g, 7) history of conditions that interfere with postural instability (e.g. cerebellar disease, vestibular disease or any others that may present), and 8) poor compliance with dialysis treatments (history of skipping \geq 2 treatments per month for $>$ 2 months). A 25-OH vitamin D level of $<$ 25 ng/ml level was chosen based on previous studies that have shown that patients have the greatest improvement in muscle strength when levels below this threshold are increased. Patients will first be identified based on the inclusion criteria, then informed about the study and consented. Those who meet the exclusion criteria will be randomized to treatment or placebo. Enrolled participants will be randomized 2:1 to receive vitamin D (n=20) or placebo (n=10) for 6 months. All participants will be tested twice over two weeks to establish baseline values. Following baseline testing, the treatment group will receive 50,000 IU (standard replacement therapy) of oral cholecalciferol or placebo. The initial dose of cholecalciferol will be 50,000 IU weekly for 6 weeks. Vitamin D levels will then be measured. Participants who still have Vitamin D insufficiency (\leq 35 ng/ml) will remain on 50,000 IU of cholecalciferol for another 6 weeks, at which point Vitamin D levels will be measured again. Participants who reach 25-OH levels $>$ 35 ng/ml will have their dosing regimen lessened to 10,000 IU weekly (maintenance dose) for the remainder of the 6 months. Participants receiving placebo will start taking the placebo maintenance dose after the first 6 weeks. For safety monitoring, 25(OH) vitamin D₃ levels will also be re-measured at monthly intervals and followed by an independent medical monitor. In patients who have serum vitamin D levels \geq 60

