Mental Status: Mini-Mental Status Exam (MMSE) (for screening), Short Blessed Test (SBT)		X							X
Executive Function: Trails B, STROOP Color-Word		X							X
Memory: California Verbal Learning Test (CVLT-II)		X							X
Attention & Processing Speed: Trails A, DS WAIS-III, SDMT, StroopColor, Stroop Word		X							X
Language: Category Fluency, Controlled Oral Word Association Test		X							X
Metabolic & Endocrine Tests	X	X	X	X	X	X	X	X	X
Vitamin D Monthly Renal Clinic labs (chart review) B12 Folate		X	X		X	X	X	X	X
Immune Function Tests serum cytokines		X							X
Demographic Data & Health Monitoring									
Age, Height, Weight, BMI, Co-morbidities, HD Hx (chart review)		X							X

Power analysis: We expect that vitamin D supplementation will improve muscular function and strength. Using information from the limited studies reported in the literature, Pfeifer, et al. (25) reported an 11% decrease in the timed up and go test for individuals treated with Vitamin D replacement therapy compared with placebo who had an average decrease. We believe our study subjects will respond in a similar manner and have powered our study such that we expect 15 of 20 subjects in the treatment group to achieve an 11% decrease in the TUG test, consistent with the Pfeifer, et. al. study findings. Similarly, postural sway has been reported by two different groups to decrease by 9% (24) and 28% (25). To be conservative, we have chosen an expected 15% decrease in postural sway in our study subjects. Muscle strength as measured by hip extensor has been reported to improve by 16% (26), and by knee extensor strength gains from 8% to 25% (25, 26). Therefore to be on the conservative side, we have

hypothesized a 10% muscle strength increase in hand grip and hip flexor strength. Only 1 of 10 in the placebo-control group is anticipated to demonstrate these improvements.

We estimate power for a two-sided test using a continuity correction. At an alpha of 0.05, with treatment response of 75% and placebo response of 10%, we estimate 90% power for a sample size of 26; 80% power with a sample size of 22 and 70% power for a sample size of 18. We are proposing a sample of 30 permitting 33% drop out to permit us to maintain reasonable power for a pilot study.

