The primary analysis for functional and cognitive outcomes will use the responder analysis described above. Additional secondary analyses will be performed on the primary outcome variables. In the first analysis, the percent change variables will be used for the group comparisons and analyzed by one-way analysis of variance (ANOVA) ($Y_1 = \%$ change; $X_1 = \text{Group}$). The percent change variable has the advantage of being easily analyzed in an analysis of covariance (ANCOVA) model if controlling variables are identified. For example, years on hemodialysis (HD y) may be need to be controlled for and as such this model would be $Y = \%$ change; $X_1(\text{HD y}) + X_2(\text{Group})$. The second analysis to be performed on the primary outcome variables will be the more traditional two-factor mixed model (2x3 table), where the between factor is Group (treatment, placebo) and the repeated measures (i.e. the within-subjects) factor is Time (BL, 3 and 6 months). In the case of missing data we will use 2 imputation methods. First as is commonly done in clinical trials of cognitive impairment and dementia we will use the last observation carried forward for missing terminal visits. We will compare results from these methods with a variety of other imputation methods. For missing data within a specific test, we will assign the average the remaining domains for those that do not complete a domain. Other imputations will include assigning values from 1) a regression across the available time points, and 2) assigning the average value of all subjects within in the group. We will compare results using these different imputations.

Significant main effects will further be explored by single degree of freedom post hoc analyses. For the secondary analyses covariates will be used including age and education adjusted T scores will be used for the baseline versus 6 month comparisons by performing a 2x2 repeated measures ANOVA. For

the self assessment variables (PASIPD and NIH PROMIS) percent change will be calculated as previously described and analyzed by one-way ANOVA as described for the primary outcome variables above.

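### H3 and H4 are worded as separate within-arm results although SA3 and SA4 ask for comparisons between randomised arms; H3 does not match its planned test, and H4 has no randomised analysis at all

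*Combined protocol and SAP*

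**What the plan says.** Section A (Specific Aims) frames both aims as contrasts between arms. SA3 is "To compare the Self-report of physical activity and quality of life (QOL) between HD participants randomized to vitamin D supplementation and placebo" and SA4 is "To compare immune function between HD participants randomized to vitamin D supplementation and placebo".

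The matching hypotheses take another form. H3 says the PASIPD total and the QOL scores "will significantly improve in the treatment groups versus no change in the control group". H4 says "immune function will be increased in the treatment group versus no change in the control group"; unlike H3, it does not mention significance. Neither gives a margin or interval for no change. H1 and H2, in the same list, are worded as a larger proportion of improvers on vitamin D than on placebo, which is a between-arm statement.

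Section C (Research Design and Methods) sets the arm sizes: "Enrolled participants will be randomized 2:1 to receive vitamin D (n=20) or placebo (n=10) for 6 months".

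The Statistical Analysis Plan in Section C treats the two sets of outcomes differently. For PASIPD and NIH PROMIS, "percent change will be calculated as previously described and analyzed by one-way ANOVA as described for the primary outcome variables above"; that earlier description has percent change as the response and Group as the factor. For the immune outcomes, the Immune Function Analysis paragraph makes the primary comparison one between subjects whose 25-OH level was above 35 ng/ml and subjects who stayed at or below it.

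**The concern.** A significant change in one arm and a non-significant change in the other do not show that the arms differ. With no definition of no change, the natural reading in 10 people is a non-significant test, and a sample of 10 often misses a real change. The 2:1 allocation adds to this: the same true change is more likely to reach significance in 20 people than in 10. A change shared by both arms, such as a placebo response on a self-report scale, could then be reported as confirming H3. Conversely, a real benefit would fail H3 as worded if placebo also improved significantly.

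For H4 the issue is more basic. Subjects above and below 35 ng/ml were not formed by randomisation. The lower group mixes placebo subjects with vitamin D subjects who did not respond biochemically. The comparison SA4 asks for is not specified.

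**Working it through.** **The plan's own figures.** The documents give no error rate, SD or expected change for the H3 or H4 outcomes. The only power statement concerns the responder analysis: "At an alpha of 0.05, with treatment response of 75% and placebo response of 10%, we estimate 90% power for a sample size of 26", with 22 for 80% and 18 for 70%. The two-sided, continuity-corrected formula for 10% against 75% gives totals of 26, 22 and 20 under equal allocation. The first two reproduce and the third is 2 higher. These figures do not bear on H3 or H4.

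**Inputs.** From the documents: 20 vitamin D, 10 placebo; alpha 0.05, two-sided (taken from the power section). Assumed: normally distributed changes with SD 1 in each arm, one-sample t-tests within each arm, and the same true mean change *d* (in SD units) in both arms, so the treatment effect is zero.

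**Probability that H3's wording is met with no treatment effect.** The arms are independent, so

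P(met) = P(significant improvement, n = 20) × P(not significant, n = 10),

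with each factor taken from the noncentral t distribution with n − 1 degrees of freedom and noncentrality *d*√n.

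| Shared change *d* | Vitamin D significant | Placebo not significant | H3 wording met |
|---|---|---|---|
| 0 | 0.025 | 0.950 | 2.4% |
| 0.1 | 0.062 | 0.941 | 5.9% |
| 0.2 | 0.134 | 0.912 | 12.2% |
| 0.3 | 0.247 | 0.864 | 21.3% |
| 0.5 | 0.565 | 0.707 | 39.9% |
| 0.6 | 0.721 | 0.604 | 43.6% |
| 0.7 | 0.844 | 0.494 | 41.6% |
| 1.0 | 0.989 | 0.197 | 19.5% |

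The maximum is 43.6%, at *d* of about 0.61. Simulation of 200,000 trials gave 40.0% at 0.5 and 43.3% at 0.6.

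**Effect of arm sizes.** With 15 in each arm the maximum falls to 25.0%, so the allocation matters. With about 13 and 7 completers, roughly what the 33% dropout allowance leaves, the maximum is 43.2%, at *d* of about 0.78.

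**The planned between-arm test.** In the same simulations the comparison of 20 with 10 rejected in 4.9-5.0% of trials for *d* from 0 to 0.7. At *d* = 0.5, H3's wording was met in 40.0% of trials, and in only 2.4% was the between-arm test also significant. The two criteria therefore disagreed in this direction in 40.0 − 2.4 = 37.6% of trials.

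**The reverse error.** As an illustration only, suppose placebo improves by 0.7 SD and vitamin D by 1.9 SD. H3's wording is met in 49% of trials, while the between-arm test of the 1.2-SD difference has 85% power.

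**H4, by comparison of text.** SA4 asks for vitamin D against placebo. H4 states a result for each arm. The Immune Function Analysis compares achieved-level groups, although its screen for confounders looks for variables that differ between treatment arms. None of these three statements specifies a randomised between-arm test of cytokine change.

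**The case against.** The strongest reply is that H3 and H4 are predictions in an aims section and not decision rules. The analysis plan contains no rule based on significance in one arm and non-significance in the other. For H3's outcomes it already specifies a between-arm ANOVA. The study is also a 30-person pilot, and these are secondary outcomes.

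Most of that stands. A reader might infer that the trial has a 40% false-positive rate for H3 and H4. The documents do not support this. The figure belongs to a criterion the plan does not adopt, and it needs both arms to improve by about 0.5-0.7 SD, which the documents neither state nor imply. It also cannot be carried over to H4, which says only that immune function will increase; the percentages would apply there only if that increase were judged by a significance test.

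What remains for H3 is that the hypothesis and its test are different criteria that can disagree, and nothing says which governs or that within-arm changes are descriptive.

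For H4, one could point to the plan's 2x2 repeated-measures ANOVA of baseline against 6 months. That sentence concerns age- and education-adjusted T scores, which Section D uses for a cognitive test, and the immune outcomes have their own paragraph. It does not fill the gap.

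**Conclusion.** The concern holds as a mismatch between hypotheses, aims and analyses. For H3 it is one of wording: the planned ANOVA holds 5%, while the hypothesis, if used as the criterion, would be met with no treatment effect in 2.4% to about 44% of trials depending on the shared change. That range assumes normal changes with equal SDs and 5% two-sided within-arm tests. For H4 it is a missing analysis: no randomised between-arm comparison of immune function is specified, and this conclusion needs no numerical assumption.

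The point is worth correcting but modest in weight. A reader might link it to the plan's statement that a positive result would lead to immediate clinical use; that statement concerns neuromuscular and cognitive function, not the H3 or H4 outcomes.

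**What to change.** 1. Reword H3 as greater improvement in percent change on vitamin D than on placebo, with improvement defined in each scale's favourable direction. Direction needs stating because PROMIS here includes pain, fatigue and emotional distress. Judge H3 only by the between-arm comparison already in the Statistical Analysis Plan, and report the difference with a 95% CI. The BDI is listed with the self-assessments but not named in the ANOVA sentence; say whether it is included.
2. Reword H4 as a between-arm difference in cytokine change from baseline to 6 months. Make that randomised comparison the primary immune analysis, and keep the comparison by achieved 25-OH level as exploratory.
3. Delete the no-change clause from both hypotheses, and add one sentence saying that within-arm changes are descriptive and will not be used to conclude benefit.

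This takes two reworded hypotheses, a revised immune paragraph and one added sentence, with no new data or patients. The cost is a lower chance of a positive result when placebo is truly stable. For a 1-SD effect at 20:10, the between-arm test has noncentrality 1/√(1/20 + 1/10) = 2.58 on 28 degrees of freedom and about 70% power; H3's present wording would be met in 0.989 × 0.950 = 94% of trials. The higher figure comes from a criterion that does not control error when both arms change.

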ng/ml, the frequency of administration will be reduced to once a month. The participants will receive supplementation for a total of 6 months. At this time, vitamin D levels will be reassessed and participants will undergo follow-up functional assessments, and cognitive and immune testing. Subjects will be recruited from the outpatient hemodialysis (HD) unit which is located on the fourth floor of the James J. Peters VAMC.

Primary Outcomes (tested at Baseline, 3 months and 6 months):

- 1) Neuromuscular functional performance using the 50ft timed walk, the TUG, a timed stair climb, and the Chair Raise test, (48)
- 2) Postural stability using a Sway meter (NeuroCom International, Inc., Clackamas, OR) that measures displacement of the body at the level of the waist in 30 second periods (49) and the Functional Reach test.
- 3) Muscle hand grip strength using the Harpenden Hand Grip dynamometer (50) and hip flexor and knee extensor strength using a Push-Pull Muscle Strength dynamometer.

Secondary Outcomes:

- 1) Cognitive function (tested at Baseline, 3 and 6 months):
 - a) Mental Status: Mini-Mental Status Exam (MMSE) (51) and Short Blessed Test (SBT) (52);
 - b) Memory: California Verbal Learning Test – II (CVLT-II) (53);
 - c) Language: Category Fluency and Controlled Oral Word Association Test (COWAT) (54);
 - d) Attention and Processing Speed: Trails A (55), Digit Span (56), Symbol Digit Modality Test (SDMT) (57), and Stroop Color and Word (58)
 - e) Executive Function: Trails B (55) and Stroop Color-Word (58).
- 2) Self-assessment of Physical Fxn and Health (tested at Baseline, 3 months and 6 months):
 - a) Physical Activity Scale for Persons with Physical Disabilities (PASIPD) (59)
 - b) NIH PROMIS (v1.0 Item Banks): Global Health Physical Function, Pain, Fatigue, Sleep, Emotional Distress (60)
 - c) Beck Depression Inventory (BDI)
- 3) Immunology (tested at Baseline, 6 months)
 - a) Serum cytokines

This study will be performed over two years.

TABLE 1. Study Flow Sheet	BL 1	BL 2	Month 1	6 weeks	Month 2	Month 3	Month 4	Month 5	Month 6
Week:	0	0 ₂	4	6	8	12	16	20	24
Physical Function Assessment 50ft walk, TUG, stair climb, Chair Raise, Functional Reach, Sway, Hand Grip, Hip & Knee Strength		X				X			X
Self - Assessment PASIPD & NIH PROMIS (short forms): Physical Fxn, Pain, Fatigue, Global Health, Sleep, Emotional Distress, BDI		X				X			X
Cognitive Impairment Tests									

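### Entry requires only 20 feet of walking, but no rule scores a patient who cannot do the primary 50-foot walk or 13-stair climb, and the missing-data methods could hide lost ability

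*Combined protocol and SAP*

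**What the plan says.** The inclusion criteria in section C, Research Design and Methods, ask that a patient be "able to ambulate independently or with an assistive device for at least 20 feet". No criterion mentions stairs or a longer distance.

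The first primary outcome, at baseline, 3 months and 6 months, is "Neuromuscular functional performance using the 50ft timed walk, the TUG, a timed stair climb, and the Chair Raise test". The description of procedures (section C, item a.2) specifies "a timed 13 stair climb".

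The Statistical Analysis Plan converts every primary measure to percent change from baseline. The primary analysis is a responder analysis. The secondary analyses of the same measures are a one-way ANOVA (or ANCOVA) on percent change and a two-group, three-time-point mixed model. The Power analysis paragraph gives responder thresholds for the TUG (11%), sway (15%), and hand grip and hip flexor strength (10%). It gives none for the 50-foot walk or the stair climb.

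For missing data the plan offers several methods:
- "we will use the last observation carried forward for missing terminal visits"
- "For missing data within a specific test, we will assign the average the remaining domains for those that do not complete a domain"
- values from "a regression across the available time points, and 2) assigning the average value of all subjects within in the group"

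It adds: "We will compare results using these different imputations". None is named as primary. No method is given for a missing baseline, and nothing says how inability to perform a test is recorded.

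**The concern.** Two primary tests ask for more than entry requires, so some patients may be unable to do them at baseline or may lose the ability during the six months. Such a patient has no time to record. That blank is itself an outcome, and the worst one the test can give. If it is not distinguished from a missed visit, the only tools in the plan are methods that supply a plausible time.

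Two things are at stake. A loss of ability can enter the analysis as stability or as average performance, and the comparison is distorted if such losses differ by arm or follow an early response. A patient who starts unable and becomes able, arguably the clearest benefit the test can show, has no percent change and drops out of the count. With 10 placebo patients, one or two such cases are visible in the result.

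**Working it through.** **Inputs.** Entry distance 20 ft, 20 vitamin D and 10 placebo patients (Research Design and Methods); 50-foot walk, 13 stairs and the TUG course (primary outcomes; item a.2); expected response 75% and 10% (Power analysis); percent change and missing-data methods (Statistical Analysis Plan).

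**The plan's own figure.** The plan has no figure on inability. The response rates used in step 4 come from its power statement, which can be checked. With equal arms, n = [1.96·√(2·0.425·0.575) + z·√(0.10·0.90 + 0.75·0.25)]² / 0.65², then n_c = (n/4)·[1 + √(1 + 4/(0.65·n))]². For 90, 80 and 70% power (z = 1.282, 0.842, 0.524), n = 9.90, 7.78, 6.42 and n_c = 12.8, 10.6, 9.2 per arm. The totals are 26, 22 and 20, against the stated 26, 22 and 18. This reproduces closely and does not bear on the present point.

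**Step 1: entry rule against test demand.** The walk is 50/20 = 2.5 times the entry distance. The TUG is 3 m out and back: 6 m / 0.3048 = 19.7 ft. The 20-foot floor therefore fits the TUG but not the 50-foot walk, and stairs have no counterpart among the criteria.

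**Step 2: what each method does with a blank time.** Let Y0, Y3 and Y6 be the times at baseline, 3 and 6 months. Percent change at month 6 is 100·(Y6 − Y0)/Y0.
- *Unable at month 6 only, carried forward:* Y6 = Y3, so the month-3 result stands.
- *Unable at months 3 and 6, carried forward:* Y6 = Y0, giving 0%.
- *Regression, assuming a straight line through the patient's own two values:* Y6 = Y0 + 2·(Y3 − Y0), which is twice the month-3 percent change. This extends an early decline, but it also doubles an early gain, and it always returns a time.
- *Group mean:* with an assumed baseline of 30 s and an assumed group mean of 20 s, 100·(20 − 30)/30 = −33%, an apparent improvement. If the mean is taken on percent change, the patient receives the arm's average effect.
- *Within-test average of remaining domains:* no clear meaning for a single timed test.
- *Unable at baseline:* Y0 does not exist, so percent change is undefined at every later visit.

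**Step 3: which analyses are affected by carry-forward.** In the responder analysis, 0% is a non-response under any threshold that requires improvement, which is the right class for someone unable. The error arises only when a month-3 responder is unable at month 6. In the percent-change ANOVA and the mixed model, 0% or the month-3 value replaces a loss of ability for every such patient.

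**Step 4: size.** With all randomized patients in the denominator, one misclassified patient moves the placebo rate by 1/10 = 10 points or the vitamin D rate by 1/20 = 5 points.

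As an illustration, suppose a share u of each arm becomes unable after month 3, independently of month-3 response, and the 75% and 10% rates apply at month 3. Carry-forward leaves the difference at 65 points. Scoring the unable as non-responders gives 75(1 − u) − 10(1 − u) = 65(1 − u), so carry-forward adds 65u points. For an assumed 1 to 3 of 30 patients (u = 3.3% to 10%), that is 2.2 to 6.5 points.

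**The case against.** A reader might infer that the plan gives every patient who becomes unable an earlier and better score. The documents do not support that. Carry-forward is worded for missing terminal visits, and a patient who attends but cannot finish the walk has not missed a visit. The plan never says inability is treated as missing; it is silent. Carry-forward is also one of several methods to be compared. A group mean is not an earlier score, a regression can project a decline, and a carried-forward month-3 value may itself be poor. The primary analysis is largely protected, because a carried-forward baseline counts as non-response.

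The stakes are also limited. This is a feasibility pilot with many primary measures. Neither test appears in hypothesis H1, which names postural sway, or in the power calculation. The point sizes refer to a response rate that the plan does not define for these two tests, and no inability rate is given anywhere.

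All of that stands and limits the claim. It does not remove it. Comparing carry-forward, regression and group mean does not help when none of them can represent inability, and the gap at baseline is not covered by any method.

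**Conclusion.** The point holds as a missing scoring rule with a foreseeable consequence. The entry rule falls short of two primary tests, inability is not defined as an outcome, and the listed imputations, if applied to a blank time, would record lost ability as no change or as average performance. A patient unable at baseline cannot be scored at all.

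The size is bounded but not known: at most 10 points of the placebo response rate or 5 points of the vitamin D rate per misclassified patient, assuming all 30 are analysed and a responder threshold is set for these tests. The 2.2 to 6.5 point illustration rests on an assumed frequency and on rates borrowed from the power section. The direction of any bias depends on how inability falls across the arms, which the documents do not tell us. This is a minor improvement rather than a threat to the trial, and it does not show that the eligibility criterion is wrong.

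**What to change.** - On the assessment form, record for each test whether it was completed, could not be performed, or was not done for another reason, so that *unable* is kept apart from *missing*.
- In the responder analysis, count unable at follow-up as non-response. State a responder threshold for the 50-foot walk and the stair climb, and state how a patient who goes from unable to able is classed; counting this as a response is the natural choice.
- In the continuous analyses of these two tests, use speed with unable set to 0, adjusted for baseline speed, in place of percent change, which stays undefined when the baseline is 0. Alternatively, use a rank test with unable as the worst rank.
- State that carry-forward, regression and group-mean imputation do not apply to inability.

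Eligibility, sample size and visits can stay as they are. The cost is one form field and a paragraph in the Statistical Analysis Plan, with results reported as speeds or ranks rather than seconds. With 10 placebo patients a single zero speed can move the arm mean, so the rank analysis is a useful check if speed is the main choice. The field should be in place before assessments, because the reason for a blank time cannot be reliably recovered later.
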